8.2 SAFETY PARAMETERS

- Incidence of cumulative ocular serious adverse events defined per ISO 11979-7.

The incidence of all other adverse events will also be presented.

8.2.1 ADDITIONAL SAFETY ANALYSES

The safety outcomes will be summarized descriptively for all eyes that have the procedure attempted.

BCDVA

Monocular BCDVA will be presented with the number and percent of eyes who fall into each category of BCDVA at each visit (e.g. 20/20 or better, 20/25 or better, 20/32 or better, etc.). The mean BCVDA letter score will be calculated for each visit. Change in BCVDA from Postop Week 3 or from Preoperative will be presented at each visit as categorical outcomes of “Increase in 15 letters or more”, “Increase in 10-14 letters”, “Increase in 5-9 letters”, “No change”, “Decrease in 5-9 letters”, “Decrease in 10-14 letters”, and “Decrease in 15 letters or more”.

Intraocular Pressure (IOP)

The IOP and change in IOP from preoperative will be summarized by mean, standard deviation, median, minimum and maximum. The number and percent of eyes reported with $IOP \geq 25 \text{ mmHg}$ or an IOP increase of $\geq 10 \text{ mmHg}$ from preop will be provided at each visit.

Slit Lamp Examination and Fundus Examination Findings

The outcomes will be summarized descriptively by count and percent of eyes with each possible finding category.

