5 OUTCOME PARAMETERS

The following visual performance parameters will be collected and summarized for subjects that received only spherical/sphero-cylindrical adjustments.

- % of eyes with UCDVA of 20/20 or better at Postop Month 1-2 and the Postop Month 3 or later visit.

The following visual performance parameters will be collected and summarized for subjects that were bilaterally implanted with the LAL and received a presbyopia adjustment.

- Proportion of subjects simultaneously with (1) Binocular UCDVA of 20/20 or better and (2) Binocular UCIVA of 20/25 or better and (3) Binocular UCNVA of 20/40 or better at Postop Month 1-2 and the Postop Month 3 or later visit.
- Change in pseudoaccommodation (D) at Postop Month 1-2 and the Postop Month 3 or later visit from pre-light adjustment at Postop Week 3

Additional analyses may be performed. Clinical data for subjects receiving only spherical/sphero-cylindrical adjustments and subjects receiving a presbyopia adjustment will be summarized and analyzed separately.

SAFETY PARAMETERS

- Incidence of cumulative ocular serious adverse events defined per ISO 11979-7.

The incidence of all other adverse events will also be presented.

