6.1 REQUIRED INCLUSION CRITERIA

- Must sign a written Informed Consent form and be willing to undergo cataract surgery for unilateral or bilateral implantation of the LAL.
- Between the ages of 40 and 80 inclusive on the day the cataract surgery is performed.
- Study eye must have preoperative keratometric cylinder ≤ 3.50 D.
- Study eye must have a cataract causing reduction in best corrected distance visual acuity (BCDVA) to a level of 20/32 or worse with or without a glare source.
- Study eye must have BCDVA projected (by clinical estimate based upon past ocular history or retinal exam) to be 20/20 or better after cataract removal and IOL implantation.
- If only one eye of a subject is enrolled, the non-study eye must have the potential for BCVDA of 20/40 or better.
- Study eye has clear intraocular media other than cataract.
- Willing and able to comply with the requirements for study specific procedures and visits.
- Study eye has a dilated pupil diameter of ≥ 7.0 mm.
- Study eye has an undilated distance viewing pupil diameter > 2.5 mm.
- Study eye requires an IOL power within the range available for the LAL.

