7.3.2.1 Postponement of Light Treatment Procedure(s)

LDD treatment should be delayed if any of the following new symptoms or changes in performance are noted;

- Best Corrected Distance Visual Acuity: With any loss of BCDVA (unless the cause is known to be non-retinal) of 10 letters or more on an ETDRS (logMAR) chart compared to the Postop Week 3 BCDVA, treatment should be delayed.

- If sutures were utilized at the time of surgery to close the incision wound, light treatments should not commence on the study eye until a minimum of 4 weeks after suture removal.⁹
- A study eye with an ocular adverse event that could be negatively impacted by light treatment or negatively impact the effectiveness or safety of a light treatment should have light treatments delayed until after the adverse event has subsided. This includes corneal edema and superficial punctate keratitis (SPK) (Grade 3 (moderate) or more severe), retinal conditions including diabetic retinopathy and cystoid macular edema, epithelial defect, and endophthalmitis.
- If a study eye is discovered with evidence of premature photopolymerization as evidenced as a zone on the lens surface, the investigator should contact the Sponsor for further instructions. (see [REDACTED] for additional details regarding premature photopolymerization).
- Any study eye possessing clinically significant posterior capsular (PC) haze should undergo a YAG capsulotomy procedure prior to the adjustment. A minimum of 48 hours should separate the YAG treatment from the corresponding refraction and LDD adjustment.

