Vision Quality Measurement (HD Analyzer)				X			X		X	X	
Undilated Distance Viewing Pupil Diameter	X			X					X	X	
Binocular UCDVA				X ¹					X ¹	X ¹	
Monocular uncorrected distance visual acuity (UCDVA)	X		X	X	X	X	X	X	X	X	X
Manifest Refraction	X			X	X	X	X	X	X	X	
Monocular best corrected distance visual acuity (BCDVA)	X			X	X	X	X	X	X	X	
Ocular Dominance Test	X			X							
Pseudo Accommodation Testing				X			X ²		X ²	X ²	
Mesopic binocular distance corrected contrast sensitivity testing				X					X ⁴	X ⁴	
Mesopic monocular distance corrected contrast sensitivity testing				X					X ⁴	X ⁴	
Photopic binocular distance corrected contrast sensitivity testing				X					X ⁴	X ⁴	
Photopic monocular distance corrected contrast sensitivity testing				X					X ⁴	X ⁴	
Monocular distance corrected 10% low contrast intermediate visual acuity (photopic)				X					X ²	X ²	
Monocular distance corrected intermediate visual acuity (DCIVA)				X	X ^{2,4}	X ^{2,4}	X ²		X ²	X ²	
Monocular distance corrected intermediate visual acuity (DCIVA) with +1.50 D add				X	X ^{2,4}	X ^{2,4}	X ²		X ²	X ²	

Visits	Preop	Operative	Postop Day 1	Postop Week 3	Adjustment #2 (if needed)	Adjustment #3 (if needed)	Lock-in #1	Lock-in #2 (if needed)	Postop Month 1-2	Postop Month 3 or later Visit	Unscheduled Visit ¹
Monocular uncorrected intermediate visual acuity (UCIVA)				X	X ^{2,4}	X ^{2,4}	X ²		X ²	X ²	
Binocular UCIVA				X ¹	X ^{1,2,4}	X ^{1,2,4}	X ^{1,2}		X ^{1,2}	X ^{1,2}	
Undilated Intermediate Viewing Pupil Diameter				X	X ^{2,4}	X ^{2,4}			X ²	X ²	
Monocular distance corrected 10% low contrast near visual acuity (photopic)				X					X ²	X ²	
Monocular distance corrected near visual acuity (DCNVA)				X	X ^{2,4}	X ^{2,4}	X ²		X ²	X ²	
Monocular distance corrected near visual acuity (DCNVA) with +2.50 D add				X	X ^{2,4}	X ^{2,4}	X ²		X ²	X ²	
Monocular uncorrected near visual acuity (UCNVA)				X	X ^{2,4}	X ^{2,4}	X ²		X ²	X ²	
Binocular UCNVA				X ¹	X ^{1,2,4}	X ^{1,2,4}	X ^{1,2}		X ^{1,2}	X ^{1,2}	
Undilated Near Viewing Pupil Diameter				X	X ^{2,4}	X ^{2,4}	X ²		X ²	X ²	

Intraocular Pressure	X		X	X	X	X	X	X	X	X	X
Slit Lamp Exam	X		X	X	X	X	X	X	X	X	X
Fundus Exam	X			X							
Aberrometry				X	X	X	X		X	X	
Dilated Pupil Diameter	X			X	X	X	X	X			
Adverse Events		X	X	X	X	X	X	X	X	X	X

¹ Only performed on subjects with both eyes enrolled and successfully implanted.

² Only performed on subjects receiving a presbyopia treatment.

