9 SEQUENCE OF PLANNED ANALYSES

9.1 INTERIM ANALYSES

An interim analysis may be performed. Since there are no statistically based hypothesis driven endpoints or associated sample size, no multiplicity adjustment is needed.

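### Does leaving the baseline for the BCDVA change table open allow the gain from cataract removal to hide a later loss?

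*Combined protocol and SAP*

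**What the plan says.** Section 8.2.1 plans three summaries of best corrected distance visual acuity (BCDVA). The first is a distribution by acuity level: "Monocular BCDVA will be presented with the number and percent of eyes who fall into each category of BCDVA at each visit". The second is the mean letter score at each visit. The third is the change table: "Change in BCVDA from Postop Week 3 or from Preoperative will be presented at each visit as categorical outcomes of" seven groups, running from a gain of at least 15 letters to a loss of at least 15 letters. Two baselines are joined by 'or', and no visit is tied to either.

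In the same section, intraocular pressure has one baseline: "The IOP and change in IOP from preoperative will be summarized".

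Elsewhere the protocol takes Week 3 as the reference for what happens after light treatment starts. Section 5 measures change in pseudoaccommodation "from pre-light adjustment at Postop Week 3". Section 7.3.2.1 judges a loss of 10 letters or more "compared to the Postop Week 3 BCDVA, treatment should be delayed". Section 7.3.2 places the first adjustment at the Week 3 visit.

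Section 9.1 states that "there are no statistically based hypothesis driven endpoints or associated sample size".

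**The concern.** The two baselines answer different questions. Change from Week 3 covers the light-treatment period alone. Change from Preoperative adds the gain from removing the cataract, and the entry criteria make that gain likely. Section 6.1 requires a cataract "causing reduction in best corrected distance visual acuity (BCDVA) to a level of 20/32 or worse with or without a glare source" and a projected acuity of 20/20 or better after surgery.

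Section 10.6 lists worse vision after adjustment or lock-in as a risk of the device. The change table is the only stated output that shows letter change within an eye. If it were run against Preoperative alone at the later visits, an eye that lost two lines after light treatment could be counted as stable or even improved. The single baseline given for intraocular pressure makes the open wording for BCDVA look like an oversight.

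**Working it through.** The plan gives no figure to reproduce here. The check has two parts: how large the offset could be, and which readings of the sentence would allow it.

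**Size of the offset**

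Inputs from the documents: entry at 20/32 or worse with or without glare, and projected 20/20 or better after surgery (Section 6.1); the letter groups (Section 8.2.1).

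Assumptions: exactly 20/20 at Week 3; 5 letters per 0.1 logMAR line; scores rounded to whole letters. Gains and losses both start at 5 letters in the list of groups, so *no change* is taken as −4 to +4.

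- Gain from Preoperative to Week 3 = 50 × log10(preoperative denominator / 20).
- Change from Preoperative at a later visit = that gain − letters lost since Week 3.

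For an eye that loses 10 letters after Week 3:

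| Preoperative BCDVA | Gain to Week 3 | Change from Preoperative | Group from Preoperative | Group from Week 3 |
|---|---|---|---|---|
| 20/20 | 0.0 | −10.0 | loss of 10–14 | loss of 10–14 |
| 20/25 | 4.8 | −5.2 | loss of 5–9 | loss of 10–14 |
| 20/32 | 10.2 | +0.2 | no change | loss of 10–14 |
| 20/40 | 15.1 | +5.1 | gain of 5–9 | loss of 10–14 |
| 20/50 | 19.9 | +9.9 | gain of 10–14 after rounding | loss of 10–14 |

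For a 15-letter loss, 20/32 gives 10.2 − 15 = −4.8 (loss of 5–9 after rounding) and 20/40 gives 15.1 − 15 = +0.1 (no change). From Week 3, both fall in the group for a loss of 15 or more.

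The arithmetic of the concern is therefore right. The first two rows matter too: an eye may qualify only under glare. If its acuity without glare was 20/20, nothing is offset. The preoperative distribution is not given, so the share of eyes in each row is unknown.

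**Which readings allow it**

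Table 1 schedules BCDVA at Preop, Week 3, Adjustment #2, Adjustment #3, Lock-in #1, Lock-in #2, Month 1-2 and Month 3 or later. There is none at the operative visit or on Day 1. So:

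1. At Week 3, only Preoperative can be the baseline.
2. Week 3 can be a baseline only at the six visits after it.
3. If Preoperative alone were used at those six visits, the reference to Week 3 in Section 8.2.1 would apply nowhere.

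Three readings remain:

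- *Preoperative at Week 3, then Week 3 afterwards.* Each named baseline has a use. A later loss appears in full.
- *Both baselines shown wherever both exist.* Each has a use. A later loss appears in full in the table from Week 3.
- *Preoperative alone throughout.* The baseline named first has no use. Only this reading allows the offset in the table above.

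The first two also agree with the use of Week 3 as the reference in Sections 5 and 7.3.2.1.

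**The case for a change.** The strongest reply is that 'or' can be read as a free choice. Nothing written forbids Preoperative alone, and the choice could be made after data have been seen, since Section 9.1 allows an interim analysis. The rule in Section 7.3.2.1 produces no table, and no light treatment is scheduled after the final lock-in, so it does not cover the last two visits. The other BCDVA outputs are group summaries. For illustration, if 10 eyes of the maximum 200 each lost 10 letters, the mean would fall by only 10 × 10 / 200 = 0.5 letter. One event to be reported as an adverse event after Week 3 is blacked out in Section 10.1, so adverse-event reporting cannot be relied on to fill the gap.

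Much of this stands. The sentence does leave the rule unwritten, and neither the acuity levels nor the mean letter score shows change within an eye. The redacted event counts neither for the plan nor against it.

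It does not follow that the plan is faulty. A free choice of Preoperative alone sets aside a baseline that the authors named, and goes against the use of Week 3 elsewhere in the protocol. The contrast with intraocular pressure is weak: acuity is changed both by the surgery and by the light treatment, which is a good reason to name two baselines. A late choice of baseline would also bias no test, because there is none, and it could be checked against the eye-level data.

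**Conclusion.** No change is needed. Section 8.2.1 leaves out a visit-by-visit baseline rule, but the visit schedule and the protocol's own use of Week 3 lead an analyst to Preoperative at Week 3 and to Week 3, or both baselines, afterwards. Either way, a loss after light treatment is shown.

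Under the one reading that would hide it, a 10-letter loss moves to *no change* for an eye at 20/32 before surgery and to a gain of 5–9 letters for an eye at 20/40. Those results assume 20/20 at Week 3 and 5 letters per line. An eye whose preoperative acuity without glare was 20/20 shows no offset. The number of eyes concerned cannot be derived.

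The consequence is small in any case. The table is descriptive, the study tests no hypothesis, and no sample size or error rate depends on it. BCDVA is scheduled at both baselines and at all six later scheduled visits, so either version of the table can be produced from data already planned. The conclusion rests on reading the sentence so that both named baselines are used.

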9 SEQUENCE OF PLANNED ANALYSES

9.1 INTERIM ANALYSES

An interim analysis may be performed. Since there are no statistically based hypothesis driven endpoints or associated sample size, no multiplicity adjustment is needed.

9.2 FINAL REPORT

When all enrolled study eyes have completed the Postop Month 3 or later visit or have been discontinued from the study, the data will be analyzed for a final study report.

10 ADVERSE EVENTS

Throughout the study, adverse events are to be documented and reported on Adverse Event Forms (AE Forms) that are included in the study documentation. If an adverse event (AE) occurs, the first concern will be the safety and welfare of the subject; treatment should be provided as appropriate for the event. During the study, the Investigator should appropriately treat and follow each AE until it resolves, stabilizes, or it is determined that further improvement is not expected.

10.1 ADVERSE EVENT (AE) DEFINITIONS

An adverse event is any untoward medical occurrence, unintended disease or injury, or untoward clinical signs (including abnormal laboratory findings) in subjects, users, or other persons, whether or not related to the investigational medical device.

Note 1 to entry: This definition includes events related to the investigational medical device or the comparator.

Note 2 to entry: This definition includes events related to the procedures involved.

Note 3 to entry: For users or other persons, this definition is restricted to events related to investigational medical devices.

The specific event should be reported as an AE:

- An [REDACTED] at any time after Postop Week 3.

10.2 ADVERSE DEVICE EFFECT (ADE) DEFINITION

Adverse event related to the use of an investigational medical device.

Note 1: This definition includes adverse events resulting from insufficient or inadequate instructions for use, deployment, implantation, installation, or operation, or any malfunction of the investigational medical device.

Note 2: This definition includes any event resulting from use error or from intentional misuse of the investigational medical device.

10.3 DEVICE DEFICIENCY (DD) DEFINITION

Inadequacy of a medical device with respect to its identity, quality, durability, reliability, safety or performance. Note: Device deficiencies include malfunctions, use errors, and inadequate labeling.

10.4 SERIOUS ADVERSE EVENT (SAE) DEFINITION

Serious Adverse Events are AEs that lead to:

- death
- a serious deterioration in the health of the subject that:

- results in a life-threatening illness or injury
- results in a permanent impairment of a body structure or function (e.g., blindness)
- requires in-subject hospitalization or prolongation of existing hospitalization
- results in medical or surgical intervention to prevent permanent impairment to a body structure or a body function
- fetal distress, fetal death, or a congenital abnormality or birth defect
- a potentially sight-threatening condition
- or is another important medical event.

10.4.1 IDENTIFICATION AND COLLECTION

All AEs that occur during the study must be recorded in English on the adverse event Case Report Form. Each event must be on a separate form, regardless of whether one event may be secondary to another or from a single cause. Identification and collection of an AE begins after informed consent has been obtained and documented. Standard sources of identifying AEs include:

- direct observation by the Investigator or study team member
- asking the study participant a specific question (e.g., “Since your last visit, have you experienced any problems with your eyes or vision?”)
- unsolicited volunteering of information by the study participant (e.g., “Doctor, I have had numerous headaches since I started using this lens.”)

Ocular AEs and SAEs and systemic SAEs observed or elicited by the Investigator, reported by the subject, or resulting from a test result, etc., occurring during the clinical investigation must be documented. AE Forms are to be completed at the time of the event regardless of all data being available.

During the study, the Investigator should treat the study subject as appropriate to ensure his/her safety and welfare. Refer to Section 7.7.1 for additional information pertaining to ongoing AEs at subject exit.

Pre-existing conditions will not be considered AE/SAEs but will be collected at the Preoperative Visit as medical history. A worsening of a pre-existing condition during the study should be documented as an AE and evaluated accordingly.

Hospitalization is a criterion for assessment of seriousness. Hospitalization in the absence of a medical AE is not in itself an AE. For example, the following reports of hospitalization without a medical AE should not be considered either an SAE or an AE:

- Planned hospitalization for a pre-existing condition without serious deterioration in health (e.g., planned knee replacement surgery)
- Social admission (e.g., subject has no place to sleep)
- Administrative admission (e.g., for yearly physical exam or elective procedures not related to the study)

- Optional admission not associated with a precipitation medical AE (e.g., for elective cosmetic surgery)

10.4.2 EVALUATIONS

When evaluating AEs, the Investigator must determine if the event is serious, assess the severity of symptoms, the relationship of the event to the device or study protocol, using the following guidelines:

1. Severity

Mild: subject awareness of a sign or symptom that is easily tolerated, requires no treatment, and does not interfere with subject's daily activities

Moderate: subject awareness of a sign or symptom which may be a low level of concern to the subject and may interfere with daily activities, but can be relieved by simple therapeutic care

Severe: a sign or symptom that interrupts the subject's daily activity and requires systemic therapy or other treatment

2. Relationship (Causality) to Study Device or Study Protocol

Related: There is at least a reasonable possibility that the AE/SAE is related to the study device or study protocol. Reasonable possibility means that there is evidence to suggest a causal relationship between the study device or study protocol and the AE.

Unrelated: There is little or no reasonable possibility that the AE/SAE is related to the study device or study protocol. This assessment implies that the AE/SAE has little or no temporal relationship to the study device and/or a more likely or certain alternative etiology exists.

10.4.3 SAE/UNANTICIPATED ADVERSE DEVICE EFFECT (UADE)/UNANTICIPATED SERIOUS ADVERSE DEVICE EFFECT (USADE) REPORTING

The site should report any event to the Sponsor and its representative in an expedited manner if it meets the criteria for an SAE and/or is an IOL explant from a study eye. Expedited reporting is calling or e-mailing the Sponsor and its representative within 48 hours of becoming aware of the event. Contact details are as follows:

Email: [REDACTED]

Tele: [REDACTED]

When reporting an SAE to the Sponsor and/or its representative, the site should forward any supporting documents along with the SAE Report Form to the Sponsor and its designee within 5 days of the initial communication. Sites must also report the SAE to the reviewing Ethics Committee per its reporting procedures.

An investigator shall submit to the Sponsor and to the reviewing IRB/EC a report of any Unanticipated Adverse Device Effect (UADE) occurring during an investigation as soon as

possible, but in no event later than 10 working days after the investigator first learns of the effect or in accordance with National Regulations. As soon as notification of a potential UADE is received by the Sponsor, an investigation will be initiated to determine if the event is a UADE. If the event is confirmed to be a UADE, the regulatory authorities, all other participating Investigators and each reviewing IRB/EC must be notified within 10 working days of the initial report from the site, as applicable or in accordance with National Regulations. If it is determined that the UADE represents an unreasonable risk to study subjects, the study must be terminated within 5 working days following the decision, and no later than 15 working days after first learning of the UADE or in accordance with National Regulations.

10.4.4 DEVICE DEFICIENCY (DD) REPORTING

All device deficiencies (DDs) should be reported to the Sponsor without unjustified delay. The Investigator is responsible for notifying the regulatory authorities and IRB/EC of DDs that could have led to a Serious Adverse Device Effect (SADE), if required by the national regulations or by the IRB/EC per each body's reporting procedures. In the case of DDs that could have led to a SADE, the Sponsor will determine whether the risk analysis needs to be updated and assess whether corrective or preventative action is required.

